# 6.3 Hypothesis to be tested

Usual HV services supplemented by the SC package is more clinically effective and costeffective than usual services alone in improving the mental health and coping of parents/carers with an excessively crying infant up to 20 weeks of age.

# 7 TRIAL DESIGN AND SETTING

Cluster Randomised Controlled Trial following CONSORT and Ottawa guidelines for such trials.

The proposed trial is in two phases: the pilot and main phase. The trial will run an internal pilot to prove recruitment of the relevant number of participants during 9 months from approximately 20 clusters.

#### Agreed Stop-go criteria:

- Randomise 20 Clusters (HV Teams) from 2-4 sites.
- Train and certify 10 SC Trained HVs to deliver the Surviving Crying CBT based sessions to parents.
- Achieve participant recruitment (target 56 participants) at an average rate of 0.4/cluster/month.

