**Design & Timelines:** Multi-centre (8- 10 sites) cluster (HV teams) randomised controlled trial with an internal pilot. The sample size is designed to detect a 2-point difference in mean EPDS score (10.5 for the control group and 8.5 for the intervention group). With a 5% level of significance (two-sided) 90% power, allowing for attrition and cluster trial methods, this gives a total target sample size of 86 clusters (43 per arm) and 392 participants (196 per arm).

**Pilot Phase: (Progression Criteria)** 56 participants to be recruited from approximately 20 clusters (10 intervention and 10 control) recruited in 9 months. SC package plus usual NHS HV services or control service usual NHS HV services, delivered to 56 participants with an excessively crying infant. SC Trained HVs will be trained and certified in delivering the SC package and procedures implemented to avoid participant bias in intervention and control groups.

**Main Trial:** If progression criteria are met, the trial will be extended to the planned number of clusters, HVs and participants.

**Dissemination:** We will work with NHS and Social Care administrative and commissioning groups and networks (CRN, PHE, iHV) throughout the trial. We will disseminate via conferences, peer-reviewed publications, clinical networks, media and social media.

Outcomes: (1) Evidence-based NHS services for parents distressed by their infant's excessive crying; (2) improved parental coping, reduced parental depression, improved infant outcomes, enhanced health visiting as an evidence-based profession; improvement in how NHS money is spent; (3) The SC website, booklet, made freely available at the end of the trial.

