#### Progression:

**GO:** 100% of target achieved **REVISE**: At least one target falls below 100% but achieves at least 80% **STOP:** At least one target falls below 80%

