# 9 TRIAL PROCEDURES

# 9.1 Cluster Identification

The sites participating in the trial have been chosen to represent diverse urban and rural settings and socio-economic and cultural groups. HV teams within sites vary in size and the communities they serve. Therefore, with their clinical leaders, we will identify the team(s) that will form a cluster within the trial, comprising of HVs working closely together. Consent to randomise a cluster will be sought. These HV team clusters will be randomised between control (usual HV services) and intervention (usual plus SC services) groups.

Randomisation of a HV team cluster will occur when the first participant is consented from that team cluster. Within each site area, we will ensure that socioeconomically diverse and minority, as well as majority, communities, are represented. As well as using the NIHR BAME Toolkit  to involve and recruit minority groups in culturally appropriate ways, we will include a sub-study directly aiming to improve these groups' involvement in the trial. We will also work with our PPI Co-applicant and collaborators to refine our recruitment methods and ensure that they recognise community as well as scientific priorities.

The target recruitment rate (estimated from the feasibility study data) will be on average 0.4 participants per month per cluster, across all clusters. Feasibility data indicated the incidence of excessive crying babies is around 20%; of those asked to participate the consent rate was around 60%. Each site will have varying birth rates, however, and the recruitment rate will be partly determined by the blinded researcher team capacity to contact, consent and assess potential participants in each of the sites and HV team clusters.

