Calculating the sample size required for a cluster randomised trial involves inflating the estimated sample size of 280 assuming individual randomisation by a design effect.  $^{\rm 39}$ 

Assuming an average cluster size of 4 with data available for the primary analysis, with a range of 2 to 12 giving coefficient of variation equal to 0.625 and ICC of 0.037 (observed in 40 results in a design effect of 1.17 (using equation 18 in ). Inflating 280 by 1.17 gives a target sample size of 328 (164 per arm). Furthermore, a sample size of 328 and 4 participants per cluster would require a total of 82 clusters to be randomised (41 per arm). Standard convention means we add 1 cluster per arm to allow for the use of the t distribution.  and 1 extra cluster per arm is also added to account for potential whole cluster drop out.  The sample size is further inflated by 12% to allow for individual loss of data and non-compliance with the primary outcome (data loss occurred in 9% of participants in our feasibility study , but we chose a more conservative rate). Therefore, each cluster should recruit 4.55 participants on average to allow for drop out (our projections show clusters could recruit an average of 4.8 so this is feasible). This gives a total target sample size of 86 clusters (43 per arm) and 392 participants (196 per arm). The effect on the sample size of assuming alternative model parameters, MCIDs, ICC values (0.01 and 0.05) and wider cluster size ranges was evaluated. These sensitivity analyses showed that the trial is robust to differences in these parameters.

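### The pilot recruitment criterion pairs 56 participants with 0.4 per cluster per month, but these agree only at an unstated mean of 7 months open, so the stop-go result is indeterminate

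*Protocol*

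**What the plan says.** Section 7 lists three stop-go criteria. One is to "Randomise 20 Clusters (HV Teams) from 2-4 sites", one concerns training and certifying 10 health visitors, and the third is "Achieve participant recruitment (target 56 participants) at an average rate of 0.4/cluster/month". The Progression paragraph then sets numerical bands: GO at 100% of target, REVISE when a target is missed but reaches at least 80%, and STOP when "At least one target falls below 80" per cent.

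The pilot's size and length appear twice. Section 7 says that it is to "prove recruitment of the relevant number of participants during 9 months from approximately 20 clusters". The Scientific Abstract has "56 participants to be recruited from approximately 20 clusters (10 intervention and 10 control) recruited in 9 months".

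Section 9.1 repeats 0.4 as the target rate, averaged over all clusters. It also says that "Randomisation of a HV team cluster will occur when the first participant is consented from that team cluster"; section 9.3 agrees. Section 14.1 needs 4.55 recruits per cluster and adds that "our projections show clusters could recruit an average of 4.8 so this is feasible".

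The protocol gives no opening schedule for the pilot clusters, no planned number of cluster-months, and no start date for a cluster's contribution to the rate.

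**The concern.** A count and a rate in the same criterion should describe the same planned performance. On the only cluster number and duration printed, they do not. Because the protocol attaches fixed percentage bands to the criterion, the gap bears on the decision to continue: what the rate reads depends on a denominator that nobody has fixed.

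The clock matters as well. A team is randomised only when its first parent consents. If cluster-months run from randomisation, every cluster starts with one guaranteed recruit, and a team that is open but recruits nobody contributes no time. The rate would then look better than the recruitment that the main phase depends on.

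**Working it through.** **Inputs.** Count 56, rate 0.4 and 20 clusters (section 7, stop-go criteria); 9 months (section 7 and abstract); STOP line 80% (Progression).

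**1. Count against rate at full exposure.**
- Cluster-months: 20 x 9 = 180.
- Participants implied by the rate: 0.4 x 180 = 72, not 56.
- Rate implied by the count: 56 / 180 = 0.311, and 0.311 / 0.4 = 77.8%.

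**2. Exposure at which they agree.** 56 / 0.4 = 140 cluster-months, and 140 / 20 = 7.0 months per cluster. Clusters opening evenly over the first 4 months give 9 - 4/2 = 7, so 56 is reproduced exactly (0.4 x 20 x 7 = 56). The protocol does not state this derivation.

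**3. What 56 recruits from 20 clusters read as, if the rate is a target in its own right and the other targets are met.** Percentage of target = 56 / (20 x months) / 0.4.

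| Mean months open | Rate | % of 0.4 | Band |
|---|---|---|---|
| 9.0 | 0.311 | 77.8 | STOP |
| 8.75 | 0.320 | 80.0 | REVISE |
| 8.0 | 0.350 | 87.5 | REVISE |
| 7.5 | 0.373 | 93.3 | REVISE |
| 7.0 | 0.400 | 100 | GO |
| 6.0 | 0.467 | 116.7 | GO |

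The STOP boundary is 56 / (0.32 x 20) = 8.75 months. The cluster number is only approximate: with all clusters open for 9 months, 19 clusters give 81.9% and 18 give 86.4%. If instead 56 is the only target and 0.4 is merely the planning rate behind it, 56 is GO at any exposure.

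**4. Counting from first consent.** Assume Poisson recruitment at true rate r, with all teams open for T = 9 months. Expected recruits per team are rT. The chance of any recruit is p = 1 - exp(-rT). Expected time after first consent is T - p/r. The pooled apparent rate is rT / (T - p/r).
- r = 0.311: 2.8 / (9 - 0.939/0.311) = 2.8 / 5.98 = 0.47, which is 117% of target, against 77.8% when counted from opening.
- r = 0.25: 2.25 / (9 - 0.895/0.25) = 2.25 / 5.42 = 0.42.

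The other targets push back. At r = 0.311, 20 teams are expected to yield 20 x 0.939 = 18.8 randomised clusters, below 20. At r = 0.25 they yield 20 x 0.895 = 17.9 clusters and 0.25 x 180 = 45 recruits. In simulation, 20 such teams met both the 20-cluster and the 56-participant targets in about 2% of pilots.

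**5. Illustration for the main trial, under an assumption.** The figure of 4.8 per cluster equals 12 months x 0.4, but the protocol states no 12-month recruitment period per cluster. If that is what is meant, 0.311 gives 12 x 0.311 = 3.73 per cluster, 86 x 3.73 = 321 recruits instead of 392, and 321 x 0.88 = 283 analysable. With 283 / 86 = 3.29 per cluster, the design effect is 1 + ((1 + 0.625^2) x 3.29 - 1) x 0.037 = 1.13. The Gamma log-link formula with section 14.1's parameters then gives about 87% power, against the planned 90%. The result moves with the period: 4.55 per cluster takes 4.55 / 0.4 = 11.4 months at the target rate and 4.55 / 0.311 = 14.6 months at the lower one, so a period of about 14.6 months would leave no shortfall.

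**The case against.** The strongest reply is that there is no contradiction. Nothing in the protocol says that all 20 clusters open on the first day. Randomising 20 clusters is itself something to achieve during the pilot, each is randomised only at its first consent, and the number is approximate. The exact match at 7 months suggests that 56 was derived from a staggered opening. The criterion can also be read as a single target of 56, with 0.4 as the planning rate behind it.

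Most of this stands, and it rules out two stronger readings. A reader might infer that meeting the count of 56 triggers STOP. That needs mean exposure above 8.75 of the 9 months, which the protocol never states and its own procedures make doubtful. A reader might also infer from the clock effect that a true rate as low as 0.25 would pass. It would not, as a rule, because the 56-participant and 20-cluster targets would normally catch it; teams that recruit nobody count against the cluster target.

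The reply does not supply the missing definition. The 7 months has to be inferred, and section 9.1 calls 0.4 a target rate, so treating it as a target in its own right is a fair reading. Nor is this a detail naturally left to an analysis plan: the protocol itself fixes the percentage bands, and they cannot be applied to the rate without a denominator.

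**Conclusion.** The concern holds in limited form. The printed count, rate, cluster number and duration do not reconcile (72 against 56, or 77.8% of the rate target). They do reconcile at an unstated mean of 7 months open. With the denominator undefined and the status of count and rate unclear, 56 recruits can fall in any of the three bands.

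The arithmetic on exposure rests only on printed figures. The inflation from a first-consent clock (a true 0.31 appearing as about 0.47) assumes Poisson arrivals and all teams open for 9 months; its upward direction follows from the randomisation rule. The figures of 321, 283 and 87% are illustrative and depend on an assumed 12-month recruitment period as well as full pilot exposure.

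Severity is moderate. The rule for continuing the trial is indeterminate as written, but allocation, outcome and effect estimation are untouched, and even the illustrative loss of power is small.

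**What to change.** Amend the stop-go paragraph in section 7 to do three things.

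1. Say whether count and rate are one target or two, and which governs progression.
2. Make the figures agree. Either keep 56 and state the planned exposure of 140 cluster-months with the opening schedule behind it, or, if all 20 clusters are meant to be open for 9 months, set the count at 72, with its 80% line at 58 (0.8 x 72 = 57.6).
3. Define cluster-months as running from the date on which each team opens to referral, including teams with no recruit.

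Appendix 2 records two sites added for the main phase, so the progression decision may already have been taken. If so, the denominator that was used should be documented alongside the result.

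The cost is one paragraph in an amendment and the steering committee's agreement. The downside is that the stated target, or the rate measured against it, may look slightly less favourable.

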#### Progression:

**GO:** 100% of target achieved **REVISE**: At least one target falls below 100% but achieves at least 80% **STOP:** At least one target falls below 80%

#### 7.1 Aims of the study

The overall aim of the trial is to test the clinical effectiveness and cost effectiveness of statutory health visiting (HV) services supplemented by SC-based service compared to statutory health visiting (HV) services alone. Objectives;

- To assess ability to recruit HV teams, train HVs in the delivery of the SC intervention, and recruit parents of excessively crying infants in a 9-month internal pilot study.
- To measure the effect of the SC intervention compared to usual care in participating parents as measured with the EPDS at 8 weeks follow-up.
- To measure the effect of the SC intervention compared to usual care in participating parents in terms of secondary outcome measures.
- To evaluate the cost-effectiveness of the SC intervention compared with standard care alone.

#### **Embedded Studies**

Process evaluations within randomised controlled trials enable questions about what works, for whom and under what circumstances to be answered, so as to inform impact and implementation. Recent assessment has pointed to the value of qualitative methods in this regard. Accordingly, we will embed two studies using qualitative and quantitative methods within the main trial. Both studies will enable the views of parents to be assessed and contribute positively to the PPI aims of the trial.

# 7.2 Outcome measures

#### 7.2.1 Primary clinical outcome

Edinburgh Postnatal Depression Scale (EPDS) score is a measurement of parental depression measured at 8 weeks post baseline measures.

#### 7.2.2 Secondary outcome measures

- Edinburgh Postnatal Depression Scale (EPDS) score 16 weeks post baseline; proportion of parents/carers with EPDS score of 10 or more
- Generalised Anxiety Disorder Assessment GAD-7 Scale self-rated measure of anxiety measured at 8 and 16 weeks post baseline.
- EuroQol-5D-5L, self-rated health utility and quality of life measured at 8 and 16 weeks post baseline.
- Parental Confidence Scale (MCQ) measures the confidence of a parent/carer in their parenting role at 8 and 16 weeks post baseline.
- Crying Knowledge Scale measures knowledge of infant crying, amount of perceived infant crying, and parents/carers' ratings of how frustrating and problematic the crying is for them, at 8 week post baseline follow-ups.
- Partner Relationship Quality (CSI-4) measures the relationship satisfaction at 8 and 16 weeks post baseline.
- Health, breast–feeding maintenance will measure parental and infant health, breast-feeding persistence at 8 weeks and 16 weeks post baseline.
- Health economic measures will be assessed at 8 weeks and 16 weeks post baseline.
- Contacts with the NHS; parents' use and parents' and HVs' ratings of services to be collected and measured.

Outcome measures	Deceline Measures	0.14/1		
Outcome measures	Baseline Measures.	8 Week	16 Week	
	(Consent to study)	(From Baseline Assessment)	(From Baseline Assessment)	
		Follow up Measures	Follow Up Measure	
Visit Window	(Within 3 working days of identification of parent/carer)	(+/- 1 week within follow up due date)	(+/- 1 week within follow up due date)	
EPDS	$\checkmark$	$\checkmark$	~	
GAD7	$\checkmark$	~	~	
EQ-5D-5L	~	✓	✓	
Parenting Confidence	✓	✓	✓	
Questionnaire				

# 7.3 Outcome Measure Table

(Maternal			
Confidence			
Questionnaire)*			
Couple Satisfaction	$\checkmark$	$\checkmark$	$\checkmark$
Index (CSI-4)			
Health Economics	$\checkmark$	~	✓
Crying Knowledge Scale **	$\checkmark$	~	
Parental Sleep	$\checkmark$	$\checkmark$	$\checkmark$
Adequacy***			
Social Support ****	$\checkmark$	✓	$\checkmark$
Health, breast-	$\checkmark$	$\checkmark$	$\checkmark$
feeding			
maintenance			
Parent/HV		$\checkmark$	
Evaluation of			
Services received.			

\*. (Originally Maternal Confidence Q. replacing 'mothers' with 'parents').

- \*\*\* 8 items from Barr RG, Barr M, Fujiwara T, et al. CMAJ 2009;180. DOI:10.1503/cmaj.081419.
- \*\*\* 2 items from Pittsburgh Sleep Quality Index, following Hiscock et al. 2014

\*\*\*\* 2 items from Hiscock et al. 2014

#### **8 ELIGIBILITY CRITERIA**

#### 8.1Cluster Identification criteria

Clusters are defined as a 'team' of health visitors who work closely together to cover families in a given geographical area within an NHS or Local Authority Health Visitor services site. All HV teams that offer services to parents that have new babies are eligible to take part in the trial. Commissioners and providers of HV services for a given geographical area will be approached to take part in the trial through Clinical Research Networks, Social Services, Institute of Health Visiting networks and 'snowballing techniques'. Once a site has agreed to take part in the trial it will be asked to identify the HV teams that could potentially take part. Consent to randomise each HV team within a site is assumed to have been given once a site agrees to take part in the trial.

# 8.2 Participant Inclusion criteria

• Parents/Carers aged 18 years or older with an infant up to 20 weeks old (at time of consent), who express concern about their infant's excessive crying.

• Written informed consent

# 8.3 Participant Exclusion criteria

- Any seriously ill infant (at time of consent), requiring inpatient hospitalisation.
- Involved with any other clinical trial at the time of consent or 3 months prior.

The hospital admission would only apply at time of consent and we would not withdraw any participants where their infant was subsequently admitted to hospital after consent into the study. This information is collected at baseline and in the follow up data so can be recorded as secondary information.

# 9 TRIAL PROCEDURES

# 9.1 Cluster Identification

The sites participating in the trial have been chosen to represent diverse urban and rural settings and socio-economic and cultural groups. HV teams within sites vary in size and the communities they serve. Therefore, with their clinical leaders, we will identify the team(s) that will form a cluster within the trial, comprising of HVs working closely together. Consent to randomise a cluster will be sought. These HV team clusters will be randomised between control (usual HV services) and intervention (usual plus SC services) groups.

Randomisation of a HV team cluster will occur when the first participant is consented from that team cluster. Within each site area, we will ensure that socioeconomically diverse and minority, as well as majority, communities, are represented. As well as using the NIHR BAME Toolkit  to involve and recruit minority groups in culturally appropriate ways, we will include a sub-study directly aiming to improve these groups' involvement in the trial. We will also work with our PPI Co-applicant and collaborators to refine our recruitment methods and ensure that they recognise community as well as scientific priorities.

The target recruitment rate (estimated from the feasibility study data) will be on average 0.4 participants per month per cluster, across all clusters. Feasibility data indicated the incidence of excessive crying babies is around 20%; of those asked to participate the consent rate was around 60%. Each site will have varying birth rates, however, and the recruitment rate will be partly determined by the blinded researcher team capacity to contact, consent and assess potential participants in each of the sites and HV team clusters.

# 9.2 Identification and Recruitment

#### Participant Identification

Parent/Carers will be introduced to the trial with a leaflet that will either be sent to all Parent/Carers with their new birth letter (wherever possible) and /or provided at the first (HV) visit.

If a parent/carer raises a concern of an excessive crying infant with their Regular HV, that HV will seek verbal consent from the parent/carer for their details to be passed onto a member of the research team. Regular HV will notify the trial site specific researcher by site secure email the details of the parent/carer to be contacted.

GP's located within the recruiting site will also be able to refer parents/carers who raise a concern of an excessive crying infant at their GP review/appointment to a member of the study research staff. They will need to obtain verbal consent from the parent/carer, to provide their contact details to the research team. The GP will be asked to complete a GP referral form which will confirm the Health Visitng team that parent/carer is registered with, this will also provide confirmation that verbal consent has been obtained from the parent/carer. This referral form will be sent by secure email to the local Surviving Crying research team.

Parents/carers can also contact their local site research team directly, to find out more about the study. Researchers will ask parents/carers which Health Visiting Team (Cluster) they are assigned. For any potential participant' that the researcher is not informed of the Health Visiting Team (Cluster), they will check on their local system for this information only.

All participants taking part in the study will continue to receive Usual Health Visiting services as normal.

The study will be promoted with Study Promotional Posters, these will be displayed in several different settings such as GP surgeries in community settings where parent/carers might attend, which will also include maternity, ante-natal units and charities. Additionally promotional material will be used for social media for Charities and websites such as 'mumsnet' and 'crysis'.

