# 9.3 Randomisation

Randomisation will be managed and carried out by LCTU. To ensure HV team clusters are evenly distributed, they will be randomly allocated either to the control or intervention group on a 1:1 basis, stratified by site.

Allocation of each HV Team cluster will be carried out when the first parent/carer's informed consent is obtained in each HV team.

The regular HV will be not be notified which group their HV team has been allocated at any point during the trial.

The researcher who has performed the consent with the parent/carer and subsequently completes all assessments, will also be blinded to the allocation of each cluster and will not know which allocation an individual participant belongs to.

Any unintended unblinding by the researcher will be recorded and another assessor will complete all further assessments for that participant. At each assessment, the outcomes assessor will be asked to guess the treatment allocation of the participant.

There will be a Research Administrator team member who will remain unblinded to the allocation and will be informed by LCTU of which of the two trial arms each HV team cluster has been allocated to and which HV team cluster subsequent participants belong to. This Research Administrator team member will be responsible for informing all participants after they have attended their baseline assessment, of their arm allocation within the trial. They will also be informed that they should not disclose the results of this allocation to the researcher who is performing the follow-up visits or their regular HV. SC trained HV will be informed if a new participant is enrolled into an intervention cluster and has requested CBT to enable delivery of the intervention. The SC Trained HV whilst not openly unblinded to cluster allocations, will be aware of those participants that require them to conduct intervention delivery.

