# 9.4 Trial Allocation

Participants will be notified of which arm they have been allocated to Intervention or Control, by the Research Administrator team member. This will be performed within 1 working day of notification of the allocation of randomisation, with a telephone call, followed up by an email. At this point the participant will be reminded that that they should not disclose what arm of the trial, they have been allocated to, to any other member of the research or HV team.

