Contamination between the groups is unlikely, given the precautions taken, as described previously. Accidental prior knowledge of a HV team's trial arm allocation may bias the recruitment selection process whilst participants who are allocated to control may lose interest and withdraw from the trial prematurely. At the 8 and 16 week follow up the researcher will be asked to guess the treatment allocation of the participant. Additionally, HV team's recruitment and retention rates will be monitored and compared across the trial duration.

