# 19 Appendix 2: Amendment History

Amendment No.	Protocol version	Date issued	Author(s) of changes	Details of changes made
	no.			
NSA01.	1.1	12/05/2022	[name]	Confidential Statement removed as per NIHR request
			[name]	Added REC and ISCTRN Registry reference added.
SA01	2.0	08/07/2022	[name]	• Sponsorship of the study transferred from De Montfort University to Nottingham Trent University.
			[name]	• Minor Changes to Consent Participant Information sheets to incorporate the change above.
NSA02	3.0		[name]	Remote Consent procedure changed
	[name]	• Parent/care Information sheet amended to incorporate the change above.		
		[name]	• Amendment to intervention booklet which included change of sponsor.	
NS03	3.0		[name]	
 
Amendment to add 2 new recruiting sites for the main phase of the study.
 

NSA04	4.0		[name]	Referral procedure changed ti add in GP referrals and self referrals.
			[name]	• Amendment to parent/carer introduction letter and parent information sheet to incorporate the change above.
				• Promontial Study matrials included for the above change.
NSA05	5.0		[name]	• Removal of the wording 'Local site research team will ensure with parent/carer that their baby has received their 6 week review before proceeding any further.' from section 9.2 of the protocol
				Changes to Inclusion & Exclusion criteria
				• Added option to record interviews with laptops.

		•	Trial Participant Flow chart updated in line with changes made in NSA04

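### Most parents join a team whose arm is already fixed and known to earlier participants, yet the non-disclosure request leaves out other parents

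*Protocol*

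**What the plan says.** **Timing of allocation.** Section 9.1: "Randomisation of a HV team cluster will occur when the first participant is consented from that team cluster". Section 9.3 repeats this.

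**Who learns the arm.** In section 9.3 the research administrator is "responsible for informing all participants after they have attended their baseline assessment, of their arm allocation within the trial". The regular HV and the researcher who takes consent and does the assessments are not told. Allocation is by team, so a participant's arm is also the arm of every other parent under that team.

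**Who must not be told.** In section 9.3 participants are informed that "they should not disclose the results of this allocation to the researcher who is performing the follow-up visits or their regular HV". In section 9.4 they are reminded that "they should not disclose what arm of the trial, they have been allocated to, to any other member of the research or HV team". Neither passage mentions other parents.

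**How parents enter.** Section 9.2 has three routes: the regular HV, the GP, and direct contact, since "Parents/carers can also contact their local site research team directly, to find out more about the study". Direct contact is not limited to teams still to be allocated. Posters, charities, social media and parent websites support recruitment. The amendment history (section 19) describes NSA04 as "Referral procedure changed ti add in GP referrals and self referrals", and that entry has no date.

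**What the plan recognises.** Section 9.5 warns that accidental prior knowledge of a team's "trial arm allocation may bias the recruitment selection process". It plans to compare recruitment and retention rates by HV team and to have the researcher guess the allocation at follow-up. Section 14.3 adjusts the primary model for individual baseline EPDS and the cluster's baseline mean.

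**The concern.** In a cluster trial that recruits after allocation, two things protect comparability: recruiters do not know the arm, and prospective participants do not know it either. The protocol protects the first with care. The second rests on enrolled parents not talking to other parents, and they are never asked not to.

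The two arms also differ in what a parent would expect. Under section 9.4, intervention parents are offered the website, the booklet and CBT sessions straight away. Control parents may ask for the booklet or website only after the 16-week assessment. A parent who knows which of these applies to their team may be more or less likely to enrol.

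If that happens, the arms can differ in motivation, expectation of help or distress in ways that baseline EPDS does not fully measure, and the 8-week EPDS contrast would carry that difference. Team recruitment rates would not reveal a change in the kind of parent enrolled at an unchanged rate.

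**Working it through.** **1. The plan's own sample size (section 14.1).** Inputs: means 10.5 and 8.5; k = 3.78 and 3.06; two-sided 5%; 90% power; 4 analysed per cluster, range 2 to 12; ICC 0.037; 12% loss.

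- n per arm = (1.960 + 1.282)² × (1/3.78 + 1/3.06) / [ln(10.5/8.5)]² = 139.16, rounded up to 140; total 280, as stated.
- CV = ((12 − 2)/4)/4 = 0.625. Design effect = 1 + ((0.625² + 1) × 4 − 1) × 0.037 = 1.169, stated as 1.17.
- 280 × 1.17 = 327.6, so 328; 328/4 = 82 clusters; two more per arm gives 86.
- 4/0.88 = 4.545 per cluster, stated as 4.55; 86 × 4.55 = 391.3, stated as 392 (an even total).

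The figures reproduce, and nothing in this point affects them.

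**2. Exposure.** One participant per cluster consents before that cluster is allocated.

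- Whole trial: 392 − 86 = 306; 306/392 = 78.1%.
- Pilot (56 participants, 20 clusters): 56 − 20 = 36; 36/56 = 64.3%.
- Per arm: 196 − 43 = 153.

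**3. Who knows the arm, and which safeguard applies.**

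| Person | Knows the team's arm? | Safeguard stated |
|---|---|---|
| Regular HV | Not told | Participants asked not to tell them |
| Consenting and assessing researcher | Not told | Participants asked not to tell them; replaced if unblinded |
| Enrolled parent | Told after baseline | Asked not to tell research or HV staff |
| Prospective parent under the same team | Only if told by someone | None stated |

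The last row is the gap.

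**4. What a bias could look like (assumed values only).** Let s be the share of post-allocation intervention recruits who enrolled because they knew the arm. Let d be the difference in their 8-week EPDS that remains after baseline adjustment. Neither is in the documents.

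- Shift b = s × (306/392) × d.
- Standard error on the log scale, with no true effect and an effective 140 per arm: √((2/3.78)/140) = 0.0615, about 0.65 points at a mean of 10.5.
- z = |ln((10.5 − b)/10.5)| / 0.0615; type I error = 1 − Φ(1.96 − z) + Φ(−1.96 − z).

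| s | d (points) | b (points) | b as share of 2 points | Type I error |
|---|---|---|---|---|
| 10% | 1 | 0.08 | 3.9% | 5.2% |
| 20% | 1 | 0.16 | 7.8% | 5.7% |
| 20% | 2 | 0.31 | 15.6% | 7.8% |
| 30% | 3 | 0.70 | 35.1% | 20.3% |
| 50% | 3 | 1.17 | 58.5% | 48.5% |

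The table takes these parents to score lower, which favours the intervention. If more distressed parents were drawn in, the shift would go the other way. Even s = 20% means 0.2 × 153 = 30.6, about 31 arm-informed parents across 43 clusters that average 4.55 recruits each.

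**The case against.** The strongest reply is that the protocol is well defended and that this route adds little.

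- **Blinding covers every route.** A self-referred parent is still checked, consented and assessed at baseline by the blinded researcher, and is told the allocation only afterwards. Team-level monitoring and baseline EPDS adjustment also apply whatever the route. This stands. A reader might infer that only the HV route is protected; the documents do not support that. What blinding cannot do is govern which parents present themselves.
- **Self-referral is not the source.** HV and GP referral also begin with a parent raising a concern, so a parent who knows the arm could use either. This stands too. Direct contact and online promotion widen the opening.
- **The chain is long.** The new parent must know an earlier participant under the same team, learn the arm, realise that it applies to them, and have an infant of up to 20 weeks. No document shows how often this happens. A reader might multiply an assumed self-referral share by an assumed outcome difference and call the result the trial's bias. That is unsupported, because most self-referrers may know nothing about any arm.
- **Peer contact is not predicted.** Section 9.5 asks both groups about sharing SC materials. This is a contamination check, and the same section calls contamination unlikely.
- **Records and analyses may exist elsewhere.** HV referrals arrive by secure email and GP referrals on a form, so route may be traceable. The CRFs and SAP are not shown, so the lack of a route field or sensitivity analysis in the protocol is not itself a fault.

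What remains is protocol text: the non-disclosure request in sections 9.3 and 9.4 omits the people through whom knowledge of the arm could reach prospective participants.

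**Conclusion.** The point holds as a modest and inexpensive improvement. On the protocol's own targets, 78% of participants enter a team whose arm is fixed and, once its first participant has been told, known to at least one local parent. The only confidentiality request is directed at staff. Arm-dependent enrolment is therefore possible. Section 9.5 already names prior knowledge of the arm as a source of recruitment bias, but the stated measures would neither prevent this form of it nor clearly show it.

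Its size and direction cannot be read from the documents. The illustrations run from negligible (0.08 points, type I error 5.2%) to serious (1.17 points, 48.5%), and the larger values need shares that look high for clusters of this size. Because NSA04 is undated, the number of teams already allocated when self-referral opened is also unknown. The documents do not support concluding that the trial is biased, or that self-referral defeats its blinding.

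**What to change.** 1. In sections 9.3 and 9.4, extend the non-disclosure request to other local parents and to online parent groups.
2. At baseline, before the participant is told the allocation, record the referral route (HV, GP, self) and whether the parent knows, or believes they know, their HV team's arm. The second answer must not reach the blinded researcher. The sealed-envelope or direct-email return to the research administrator in section 9.5 would serve. Among each team's first participants any such belief is a guess, which gives a useful reference rate.
3. Add route and prior knowledge, by arm, to the recruitment monitoring in section 9.5.
4. Run a sensitivity analysis of the primary outcome that excludes participants with prior knowledge of the arm. Excluding post-allocation self-referrals should be a supplementary check only: it drops parents who came through a poster knowing nothing, and keeps informed parents who came through the HV or GP.

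The cost is one sentence in the allocation call, one or two data items, and a sensitivity analysis with fewer participants and so less precision. That analysis also has a limit: it can remove informed parents who enrolled, but it cannot recover informed parents who stayed away. The confidentiality request in item 1 is therefore the more valuable change.
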